5.1 Primary Objective

To generate real-life, in-home data from parents with infants (preterm and full-term) on sleep, stress, and infant nutrition via the study chatbot.

5.2 Secondary Objective

To investigate differences in data obtained from parents of preterm infants versus data obtained from parents of full-term infants on sleep, stress, and infant nutrition.

5.3 Exploratory Objective

To evaluate the usability of ClaimIt, the study chatbot, and chatbot tools in general, among this population.

6. Trial Design

This is an observational study of 40 parent and infant pairs (20 parents of preterm infants, 20 parents of full-term infants) residing in Singapore.

6.1 Trial Endpoints

Primary Endpoint

Obtaining records of sleep, stress, and infant nutrition from parents of infants (preterm and full-term) through interaction with the study chatbot

Secondary Endpoint

Comparison of the data obtained from parents of preterm infants and parents of fullterm infants on sleep, stress, and infant nutrition obtained via the study chatbot

Exploratory Endpoint

An evaluation of the usability of ClaimIt, the study chatbot and chatbot tools in general, among this population.

6.2 Study Population

6.2.1 Subject Inclusion Criteria

- Healthy infants (preterm [born at <37 weeks of gestation] and full-term [born at ≥37 weeks of gestation]), 0-6 months of age at time of enrollment
- Infants must be at home (discharged from the hospital) at time of enrollment
- Informed consent from the parent (whose age is ≥21 years)
- Parent must be proficient in the English language
- Parent must be able to comply with the required study tasks, as per Pl's judgment
- In-home access to reliable internet connections and a tablet and/or mobile device suitable for electronic communication

6.2.2 Subject Exclusion Criteria

To be considered for enrollment, the subjects must not meet any of the exclusion criteria listed below:

Infants:

- Known to have current or previous illnesses/conditions which could interfere with the study outcome, as per PI's clinical judgment
- Must not be currently participating in any other clinical study

Parent of infants:

- Must not be known to have a significant medical condition that might interfere with the study (per PI's clinical judgment) that meets one of the following criteria:
 - Presence of current mental illness or history of mental illness
 - Any acute or chronic illness that makes the parent (subject) unsuitable for the study based on the PI's judgment
- Must not be a single parent
- Inability of the parent to comply with the study protocol or PI's uncertainty about the willingness or ability of the subject to comply with the protocol requirements

6.2.3 Subject Withdrawal Criteria

Subjects may be withdrawn from the study at any time for any reason, including but not limited to:

- 1) At their request or the request of the legally authorized representative.
- 2) If, in the PI's opinion, continuation in the study would be detrimental to the parent or infant's well-being.
- 3) Non-compliance (failure to complete five [5] or more consecutive sessions), at the discretion of the PI (a situation where the parent consistently does not adhere to the study procedures).

4) Protocol deviation(s) which, in the opinion of Sponsor, warrant discontinuation from study (e.g., violation of inclusion and/or exclusion criteria).

A dropout of ≤10 families is built into the estimated total sample size. If the dropout threshold of 10 is reached, up to 10 additional participants may be replaced at the sponsor's discretion. The PI must make every effort to contact parents that are lost to follow-up. Attempts to contact the parent must be documented in the family's record (e.g., dates and times of attempted telephone/email contact).

The number and percentage of subjects who withdraw early and their reasons for withdrawal will be presented in a table and the equivalent of a CONSORT flow diagram.

The following information will be documented in the mother and infant/toddler's record in the event of a subject's withdrawal from the study:

- I. Date of withdrawal
- II. Reasons for withdrawal

Even if consent is withdrawn, all data that were acquired before consent was withdrawn will be maintained.

6.3 Centers

Participants will be recruited through the Department of Neonatology at KK Women's and Children's Hospital. After the screening visit, infants and parents will not be required to visit a physical trial site (unless reconsent is required). Communication between parents and study personnel will be conducted via the ClaimIt platform and/or over the telephone or email messaging, as appropriate.

7. Execution of the Trial

7.1 Chatbot Interactions During Study Period

The parent will be asked to interact with the study chatbot three times a week (e.g., Monday, Wednesday and Friday [suggested schedule]) over a maximum 28-day period. During each of those interactions, they will be asked to interact on all three topics: sleep, stress, and infant nutrition. Reminder notifications will be sent via ClaimIt for any parent that does not interact with the chatbot per protocol.

The maximum number of interactions per subject pair is 12 (in total).

7.2 Data Collection

Chatbot transcripts will be created based on each interaction between the parent and study chatbot.

eCRFs will be completed by the parent for their infant based on data from:

- the Screening eQuestionnaire
- the end-of-study Usability eQuestionnaire

7.3 Compliance

Compliance with the study expectations will be monitored through the study chatbot's regular use and reported as follows:

 Compliant: Defined as having completed a total of 7 or more interactions with the study chatbot in the 4-week study period

Note: If only seven (7) sessions are completed with the study chatbot, the five (5) missing interactions must not be consecutive

 Non-compliant: Defined as the failure to complete five (5) or more consecutive sessions in the 4-week study period

Subjects may be withdrawn from the study in the event of non-compliance.

7.4 End of Study

At the end of the study, the parent will be asked to complete an eQuestionnaire to assess and comment on the usability of ClaimIt, the study chatbot and chatbot tools in general (Appendix II). Access to the study chatbot will be discontinued, and the study team may contact the parent if there are any outstanding study related queries.

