	Secondary: Comparison of the data obtained from parents of preterm infants and parents of full-term infants on sleep, stress, and infant nutrition Exploratory: An evaluation of the usability of ClaimIt, the study chatbot and chatbot tools in general, among this population			
Study Implementation	Prescreening Participants (parents and infants [preterm or full-term]) will be recruited by study team personnel in the Department of Neonatology at KK Women's and Children's Hospital Upon successfully fitting the basic eligibility criteria, the parent will be provided: Informed Consent Form (ICF) for review The parent will have the opportunity to ask questions and receive answers from study team personnel Access to the ClaimIt app along with the following information: Overview of trial tasks and relevant notifications ClaimIt navigation instructions: How to interact with the ClaimIt app during the study period Additional study details & instructions All relevant contact information that may be required during the study			

	Screening and Enrollment				
	Upon signing the ICF, the parent will be asked to respond to				
	a detailed eQuestionnaire (Appendix I) to assess eligibility				
	If all the inclusion and none of the exclusion criteria are				
	satisfied, the PI will enroll the subjects into the study				
	Upon enrollment, the parent will be provided full access to				
	the study chatbot along with the following information:				
	 How to connect to the study chatbot 				
	Overview of trial requirements & parameters				
	The Chatbot navigation: How to interact with the study				
	chatbot during the 28-day period				
	Overview of notifications related to trial activities				
	Additional study details & instructions				
	Data Collection Period				
	The parent will be asked to regularly interact with the study				
	chatbot on three (3) topics, three (3) days a week (suggested				
	schedule: M, W, F) for 28 days				
	Through regular interaction with the study chatbot, records				
	of parents' sleep, stress, and infant nutrition will be obtained				
	End of Study				
	At the end of the 28-day data collection period, the parent				
	will be asked to complete an eQuestionnaire about the				
	usability of the study chatbot and ClaimIt (Appendix II)				
Statistical	A sample size of 40 parents and their infants is estimated with the				
Considerations	following considerations:				
	Descriptive summary statistics for the categorical and				

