7.1 Study Calendar

Schedule of Activities	Prescreening	Screening and Enrollment	Data Collection	End of Study
Basic study information provided to parents	Х	-	-	-
Inclusion/exclusion criteria met	Х	х	-	-
Review of Informed Consent Form (ICF) and consent provided by parent	-	х	-	-
Chatbot app and instructions provided	-	Х	-	-
28-day data collection via study chatbot	-	-	Х	-
Chatbot/ClaimIt usability eQuestionnaire	-	-	-	х

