8.1 Sample Size Calculations

A sample size of 40 subjects is estimated under the following considerations:

- Descriptive summary statistics for the categorical and quantitative data will be reported
- Expected dropout rate of ≤10 subjects (if the dropout threshold of 10 is reached,
 up to 10 additional participants may be replaced at the sponsor's discretion)
- A subject will be considered to have dropped out if they are determined to be non-compliant; however, qualifying chatbot interactions will be included in ITT.

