8.5 Exploratory Endpoints

The study's exploratory endpoint is an evaluation of the usability of ClaimIt, the study chatbot and chatbot tools in general, among this population.

To accomplish this analysis, descriptive statistical analysis will be performed on each question of the Usability of Chatbot and ClaimIt eQuestionnaire. Questions will be analyzed for frequency and, in the case of questions that are based on Likert Scales, univariate distributions (mean, median, standard deviation, etc.).

Question 9 through 14 of the questionnaire are open-ended. Qualitative analysis will be performed on these questions where possible in order to obtain the frequencies of certain response patterns. In the case of individual answers (that do not follow a pattern) such will be presented in list form.

Tables, listings, and figures pertaining to exploratory endpoints are grouped by analysis data set (FAS and PP) in the TLF shells.

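### The usability form is scheduled only at day 28, so parents withdrawn early for not using the chatbot have no planned occasion to rate it, and FAS usability results may lean towards continuing users

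*SAP*

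**What the plan says.** **Timing of the form.** SAP 7.4 and Protocol 10.5 use the same sentence: "At the end of the study, the parent will be asked to complete an eQuestionnaire". The protocol synopsis fixes the time: "At the end of the 28-day data collection period, the parent" is asked for it, and the SAP synopsis agrees. In the Protocol 7.1 calendar, the row "Chatbot/ClaimIt usability eQuestionnaire" is marked only in the End of Study column.

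**Leaving early.** SAP 6.2.3 lists as a ground for withdrawal "Non-compliance (failure to complete five [5] or more consecutive sessions), at the discretion of the PI". SAP 7.3 repeats it as a permission: "Subjects may be withdrawn from the study in the event of non-compliance". SAP 8.1 adds: "A subject will be considered to have dropped out if they are determined to be non-compliant". That section and Protocol 11.1 expect no more than 10 dropouts among 40, with up to 10 replacements if the sponsor wishes. The items to be documented at withdrawal are the date and the reasons (Protocol 8.3, SAP 6.2.3).

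**Route.** The form is completed in the ClaimIt app, which subjects have while they are enrolled (Protocol 10.6, SAP 7.5).

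**Analysis.** SAP 8.5 states: "Tables, listings, and figures pertaining to exploratory endpoints are grouped by analysis data set (FAS and PP) in the TLF shells". The FAS needs one completed topic (SAP 8.2.2). The PP set needs at least seven interactions and the full collection period (SAP 8.2.3). The SAP text gives no rule for FAS members without a form, and its example for Table 2 (SAP 8.7.1) has all 40 parents answering.

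**The concern.** The form asks about ease of use, satisfaction, length of interactions, malfunctions and what was liked least. One of the routes out of the study is not using the tool that the form rates. A missing rating is therefore plausibly related to the rating that would have been given.

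The two analysis sets do not expose this. The PP set excludes withdrawn parents by definition. The FAS includes them if they completed one topic, but as planned it may hold no form from them. The FAS forms would then come from parents who stayed to the end, so close agreement between FAS and PP could look reassuring without saying anything about those who left.

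At stake is the exploratory objective of a pilot study. Ratings that were never collected cannot be recovered at analysis.

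**Working it through.** **1. Can a parent leave before the form is due and still be in the FAS?** Take the suggested Monday, Wednesday, Friday schedule, starting on a Monday as day 1. A parent who completes session 1 and misses sessions 2 to 6 has missed five in a row by the Friday of week 2, which is day 12. That parent completed at least one topic, so is in the FAS, and may be withdrawn 16 days before day 28. No text triggers the form at that point.

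**2. The plan's own figure.** The SAP 8.7.1 example has 30 answers of 5 and 10 answers of 4.
- Mean = (30 × 5 + 10 × 4)/40 = 4.75.
- Sample SD = √[(30 × 0.25² + 10 × 0.75²)/39] = √(7.5/39) = 0.4385, rounded to 0.44.

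Both figures reproduce. The example assumes complete response.

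**3. Effect of missing raters.** Bias of the raters' mean = (non-raters/all) × (mean of raters − mean the non-raters would have given). The documents give 40 parents and at most 10 dropouts, so the fraction is at most 10/40 = 0.25 without replacement. They give nothing on how non-raters would score, so every gap below is an assumption.

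| Non-raters / enrolled | Gap (points) | Bias (points) |
|---|---|---|
| 10/40 | 1 | 0.25 |
| 10/40 | 2 | 0.50 |
| 10/40 | 0 | 0 |
| 10/40 | −0.5 | −0.125 |
| 5/40 | 1 | 0.125 |
| 2/40 | 1 | 0.05 |
| 10/50 (all 10 replaced, 40 raters) | 1 | 0.20 |

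For example, if 30 raters average 4.75 and 10 non-raters would have averaged 3.75, the mean over all 40 is (30 × 4.75 + 10 × 3.75)/40 = 4.50. The reported value is then 0.25 too high. Replacement reduces the bias but does not remove it.

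**4. Denominator.** The table uses all enrolled parents. Dropouts who completed no topic are outside the FAS, and the documents do not say how many there would be. If, say, 5 of the 10 were outside, the FAS fraction is 5/35 = 0.14, and a 1-point gap gives a bias of 0.14.

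**5. Malfunction rate.** If 10% of 30 raters and 50% of 10 non-raters had a malfunction (assumption), 10% is reported where the rate over all 40 is (3 + 5)/40 = 20%. Favourable selection lowers this figure. It also lowers the mean of question 15, where 5 means very worried.

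**The case against.** A reader might infer two stronger conclusions, and the documents support neither.

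**That withdrawn parents never rate the chatbot.** Withdrawal for non-compliance is optional and left to the investigator. A non-compliant parent who is kept in can reach the end-of-study form. SAP 7.4 does not limit the form to completers, and SAP 7.5 speaks of completion by each parent. The documents are silent on withdrawn parents; they do not bar them. What remains is that no occasion is planned for them and that the app is described as available only during enrolment.

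**That usability results are biased upward.** Nothing in the documents shows that dropouts would rate lower. Parents may stop for lack of time or because of infant care. Withdrawal also covers parental request, well-being and eligibility violations, which need not reflect usability. Upward is also the wrong direction for question 15 and for malfunction rates.

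It is also tempting to set the possible bias against a standard error built from the example SD of 0.44. That SD belongs to an illustration with mean 4.75 and does not carry over to other means. At a mean of 4.5 on a whole-number item, the smallest sample SD with 30 raters is about 0.51. No inference is planned on these items, so the comparison is best left out.

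Some of the issue is handled elsewhere. Withdrawals and their reasons are tabulated and shown in a flow diagram, and the investigator must try to contact parents lost to follow-up. The table shells are a separate document, so whether they carry a respondent count cannot be judged here. These provisions show how many left and why, but they collect no ratings. Usability assessment at the end of a study is also a common choice, and the endpoint is exploratory and descriptive, which limits the weight of the point.

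**Conclusion.** The gap is real and limited. The plan has one usability administration, at the end of 28 days, and none at early withdrawal, while one ground for withdrawal is non-use of the chatbot. FAS usability results may therefore over-represent continuing users and are at risk of favourable bias. Neither the size nor the sign can be established from the documents.

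The illustrative 0.25 to 0.50 points rests on three assumptions: the full 10 of 40 drop out, none of them rates, and they would have scored 1 to 2 points lower. With all 10 replaced, the 1-point case gives 0.20. Fewer dropouts, some ratings from non-compliant parents who stay, or a smaller gap would shrink these values, and no gap gives no bias. The primary and secondary endpoints use chatbot records and are not affected. The change is worth making because it is cheap and the missing answers cannot be obtained later.

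**What to change.** In Protocol 10.5 and SAP 7.4, with the synopses and the Protocol 7.1 calendar aligned:
- Offer the usability form (Protocol Appendix II; Appendix I of the SAP, although SAP 7.4 cites it as Appendix II) once per parent, at early withdrawal or at day 28, whichever comes first.
- Limit the offer to parents who still agree to answer, and keep ClaimIt access open for that form. A single form per parent avoids having to choose between two sets of answers.

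In SAP 8.5 and 8.7.1, for Tables 2-11:
- Report the number answering out of the number in the FAS.
- Show withdrawn or non-compliant parents separately.

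The cost is one extra trigger for an existing electronic form, a respondent count, and a separate display in the tables. Some withdrawn parents will not reply, which the count makes visible. Those who do will be rating a shorter exposure, which is a reason to show them apart. The protocol change needs IRB approval. If the final table shells have to be extended after the SAP is executed, SAP 10.2 requires a SAP amendment.

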7.5 Application Description

The study chatbot is an interactive, conversational application where the parent can initiate a conversation with the chatbot, and it will respond appropriately. In certain instances, the study chatbot may also initiate a conversation with parent. The application converses with the user through the messaging platform. Transcripts of the chatbot conversations will be accessed and reviewed by the study team.

Completion of the Screening and Usability eQuestionnaires will occur via the ClaimIt app for each of the parents. The ClaimIt app is a mobile application available to subjects during their period of enrollment so they can perform specific study-related tasks and receive and transmit communications from and to the CRO staff.

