8.2 Datasets to be Analyzed

8.2.1 Intent-to-treat (ITT)

All enrolled participants in accordance with the Intent-to-treat (ITT) principle.

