8.2.2 Full Analysis Set (FAS)

All ITT participants who have completed at least one topic (Sleep, Stress, and/or Nutrition).

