Appendix I: Usability of Chatbot and ClaimIt eQuestionnaire

The following is a questionnaire is for you to	provide feedback o	on your	interactions	with th
chatbot. Please pick the best answer.				

nat	bot. Please pick the best answer.
1.	Please rate the study chatbot's overall ease of use on a scale of 1 to 5:
	(Very Difficult) 1 2 3 4 5 (Very Easy)
2.	Please rate the ClaimIt application's overall ease of use on a scale of 1 to 5:
	(Very Difficult) 1 2 3 4 5 (Very Easy)
3.	How satisfied were you with your interactions with the study chatbot?
	(Very Dissatisfied) 1 2 3 4 5 (Very Satisfied)
4.	How satisfied were you with your interactions with ClaimIt?
	(Very Dissatisfied) 1 2 3 4 5 (Very Satisfied)
5.	Did the study chatbot malfunction?
	a. Yes (will be asked a follow-up question)
	b. No
	(If Yes) How did the study chatbot malfunction? [Open-ended question]
6.	Did ClaimIt malfunction?
	a. Yes (will be asked a follow-up question)b. No
	(If Yes) How did ClaimIt malfunction? [Open-ended question]
7	How likely are you to consider using a chatbot application as an interactive tool to
, .	provide input on similar topics?
	(Not at all Likely) 1 2 3 4 5 (Very Likely)
8.	How would you rate the length of interactions you had with the study chatbot?
	(Too Long) 1 2 3 4 5 (Easily Manageable)
9.	What did you like the least about the study chatbot? [Open-ended question]
10.	What did you like the most about the study chatbot? [Open-ended question]
	Page 27 of 27

11.	Do you have any other comments about the study chatbot that you would like the investigators to know? [Open-ended question]
12.	What did you like the least about the ClaimIt app? [Open-ended question]
13.	What did you like the most about the ClaimIt app? [Open-ended question]
14.	Do you have any other comments about the ClaimIt app that you would like the investigators to know? [Open-ended question]
15.	How worried were you about sharing your data with the study chatbot? (Not at all worried) 1 2 3 4 5 (Very worried)
16.	How likely would you be to use a chatbot tool like this in real life to get access to information and reassurance if you could? (Not at all likely) 1 2 3 4 5 (Very likely)
	Why or why not? [Open-ended question]

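### Parents whose tools failed completely can be missing from the usability tables, because ClaimIt is the only described questionnaire route and outputs are planned only for FAS and PP

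*SAP*

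**What the plan says.** **Route.** SAP 7.5 and Protocol 10.6 state: "Completion of the Screening and Usability eQuestionnaires will occur via the ClaimIt app for each of the parents". Neither document describes a paper, email or telephone version. The same SAP section describes ClaimIt as "available to subjects during their period of enrollment".

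**Timing.** SAP 7.4: "At the end of the study, the parent will be asked to complete an eQuestionnaire to assess and comment on the usability of ClaimIt". Nothing says whether a parent who leaves early is asked.

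**Content.** The questionnaire (SAP Appendix I, Protocol Appendix II) has 16 questions. Question 5 asks about chatbot malfunction, and Question 6 asks "Did ClaimIt malfunction". Under SAP 8.7.1 the rating items go to Table 2, the two malfunction items to Table 3, their descriptions to Tables 4 and 5, and the open answers to Questions 9 to 14 to Tables 6 to 11.

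**Analysis sets.** SAP 8.5: "Tables, listings, and figures pertaining to exploratory endpoints are grouped by analysis data set (FAS and PP) in the TLF shells". SAP 8.2.2 limits the FAS to ITT participants who finished at least one of the three chatbot topics. SAP 8.2.3 limits PP to FAS participants with at least seven interactions who stayed for the whole collection period. The SAP does have a wider set, the ITT, defined in 8.2.1 as "All enrolled participants in accordance with the Intent-to-treat (ITT) principle", but 8.5 does not name it for usability.

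**The concern.** The instrument that measures failure of the app runs on the app. A parent whose ClaimIt no longer opens at the end of study has no described way to answer Question 6. Separately, a parent whose chatbot never worked may still open ClaimIt, answer yes to Question 5 and say what went wrong. That answer would be collected and then left out, because the parent is outside the FAS.

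Other rules can add to the loss. Reminders go through ClaimIt (SAP 7.1), so a broken app may also silence them. Missing five consecutive sessions is non-compliance (SAP 7.3). Non-compliance counts as dropout (SAP 8.1) and may lead to withdrawal, while ClaimIt is described as available only during enrollment. A technical failure could thus be recorded as non-compliance with no usability answer attached.

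At stake is the exploratory objective. Missingness that depends on the outcome being measured tends to make the tools look better than they were. In a pilot of these tools, complete failures are among the most useful things to learn about.

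**Working it through.** **1. The plan's own figure.** SAP 8.7.1 gives an example for Table 2: thirty of forty parents score 5 and ten score 4.
- Mean = (30×5 + 10×4)/40 = 190/40 = 4.75.
- Sum of squares = 30×0.25² + 10×0.75² = 1.875 + 5.625 = 7.5.
- SD = √(7.5/39) = 0.4385, which rounds to 0.44.

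The example reproduces. It has all forty parents answering, although SAP 8.1 allows for up to 10 dropouts.

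**2. Who is counted.** Reading SAP 7.4, 7.5, 8.2 and 8.5 together:

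| Parent's experience | Can answer by the described route? | In FAS? | In Tables 2 to 11? |
|---|---|---|---|
| Intermittent failure, at least one topic done, ClaimIt opens at the end | Yes | Yes | Yes |
| Chatbot fails after one completed topic, ClaimIt opens at the end | Yes | Yes | Yes |
| Chatbot never works, ClaimIt opens at the end | Yes | No | No |
| ClaimIt does not open at the end, whatever came before | No | Either | No |

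The FAS threshold is low: 12 interactions × 3 topics = 36 possible topic completions, of which one suffices. A dropout with one completed topic stays in the FAS. Screening also runs in ClaimIt (SAP 7.5), so the app worked at least once for every enrolled parent.

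**3. Illustrative size.** Input from the plan: 40 enrolled. Assumptions: *m* parents are missing from the tables, 3 of the others report a malfunction, and those others average 4.75 on a rating item.
- Table 3 shows 3/(40 − m).
- The share among all enrolled lies between 3/40 (no missing parent had a malfunction) and (3 + m)/40 (all did).
- The mean among all enrolled lies between [4.75(40 − m) + 1×m]/40 and [4.75(40 − m) + 5×m]/40.

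| m | Table 3 shows | All enrolled: malfunction | All enrolled: mean rating |
|---|---|---|---|
| 2 | 3/38 = 7.9% | 7.5% to 5/40 = 12.5% | 4.56 to 4.76 |
| 4 | 3/36 = 8.3% | 7.5% to 7/40 = 17.5% | 4.38 to 4.78 |
| 10 | 3/30 = 10.0% | 7.5% to 13/40 = 32.5% | 3.81 to 4.81 |

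The row m = 10 uses the whole dropout allowance and is an extreme, since a dropout need not be missing from these tables.

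The first row fits either mechanism. If all 40 return the questionnaire but 2 who report a failed chatbot are outside the FAS, 5/40 is collected and 3/38 is tabulated.

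**The case against.** - **Most failures are still seen.** A reader might infer that every parent for whom the tools failed drops out of the result. The documents do not support that. Questions 5 and 6 look back over the study, and parents with partial failure reach Tables 3 to 5. This objection stands and limits the point to complete or terminal failure.
- **No text forbids another route.** A reader might also infer that a parent with a broken app cannot tell anyone. That too goes beyond the text. SAP 6.3 says: "Communication between parents and study personnel will be conducted via the ClaimIt platform and/or over the telephone or email messaging, as appropriate". CRO staff handle ClaimIt questions, and the monitor checks eCRF data for completeness and may contact parents (Protocol 10.7). The team may also contact parents with outstanding queries at the end of study (SAP 7.4). Withdrawal reasons are tabulated (SAP 6.2.3). These channels let a failure become known. None is stated as a way to complete the questionnaire, and no output is planned that would bring such reports into Tables 2 to 11.
- **Few parents can fall outside the FAS, and some chatbot exposure is a fair condition for rating the chatbot.** Both are true, and they are a reason to keep an FAS display. The condition does not suit the ClaimIt items, which need no completed topic, or Question 5, where never completing a topic may be the malfunction itself.
- **The sizes are constructed.** Correct. The number of missing parents and the number reporting a malfunction are assumed.
- **The table shells are a separate workbook** (SAP 10.2) that is not part of the documents, so their actual denominators could not be checked. This stands; the point rests on the wording of SAP 8.5.

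**Conclusion.** The point holds in a limited form. On the text as written, two groups can be absent from Tables 2 to 11: parents unable to open ClaimIt at the end of study, and parents with no completed chatbot topic, whether or not they answer. Complete or terminal failures are therefore under-represented. The likely direction is malfunction rates too low and ratings too high. That direction assumes that the missing parents had more trouble than the rest. If none of them had a malfunction, Table 3 would be slightly too high instead (7.9% against 7.5% in the first row of the table).

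The size is unknown. The contrast of 7.9% with 12.5% shows only that, with 40 enrolled, two missing parents can move the percentage noticeably; it is not an estimate of bias. The primary and secondary endpoints are unaffected, and no usability hypothesis or threshold depends on these tables. Priority is low to moderate: a cheap improvement to an exploratory, descriptive endpoint.

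**What to change.** 1. **Protocol 10.5 and 10.6, SAP 7.4 and 7.5:** offer the same 16 questions by email link or telephone to any parent who has not returned them in ClaimIt within a set number of days. State whether parents who leave early are asked. Record the response mode.
2. **SAP 8.5:** tabulate usability for all enrolled parents who return the questionnaire, with returned/enrolled in each table header, and keep FAS and PP as supplements. Write all enrolled parents rather than ITT, because Protocol 11.2.1 uses ITT for a narrower set that requires interaction on all three topics.
3. **Malfunctions reported to support staff:** list them separately. Do not add them to the Table 3 percentages, which would mix unsolicited reports with answers to a question put to every parent.

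**Cost.** A link or call to a few non-responders over channels already in use, plus changes to wording and table shells. The protocol change must go to the ethics committee (Protocol 12.2.3). Additions to the final shells need a SAP amendment and may affect the study contract (SAP 10.2). The statistical downside is a small mixed-mode effect, handled by flagging response mode in the tables.
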